3.2 Key Definitions

The following definitions will be used:

- Subcutaneous Fat Thickness: Subcutaneous fat thickness can be calculated by the mean of ultrasound results of subcutaneous fat thickness at 4 ultrasound scan spots on abdomen including far left, left, far right, and right spots:

$$\text{Subcutaneous Fat Thickness} = [\text{Ultrasound Result (Far Left)} + \text{Ultrasound Result (Left)} + \text{Ultrasound Result (Right)} + \text{Ultrasound Result (Far Right)}] / 4$$

- Subcutaneous Fat Volume:
 - Stage 1: Subcutaneous fat volume over treated area for each treatment group in Stage 1 will be calculated using the following formulas as suggested in the previous Caliway studies:

$$\text{CBL-514 480 mg: Subcutaneous Fat Volume(mL)} = \text{Subcutaneous Fat Thickness(cm)} \times 240 \text{ cm}^2$$

$$\text{CBL-514 640 mg: Subcutaneous Fat Volume(mL)} = \text{Subcutaneous Fat Thickness(cm)} \times 320 \text{ cm}^2$$

$$\text{CBL-514 800 mg: Subcutaneous Fat Volume(mL)} = \text{Subcutaneous Fat Thickness(cm)} \times 400 \text{ cm}^2$$

- Stage 2: Assuming the treatment area is 300 cm² (which is the area for the maximum dose of 50 injections) subcutaneous fat volume over treated area will be calculated using the following formula as suggested in the previous Caliway studies:

$$\text{Subcutaneous Fat Volume(mL)} = \text{Subcutaneous Fat Thickness(cm)} \times 300 \text{ cm}^2$$

- Baseline: The baseline value is defined as the last available valid (quantifiable continuous or categorical value), non-missing observation for each participant prior to first study drug administration. Repeat and unscheduled assessments will be included in the derivation of the baseline values.
- Change from Baseline: The change from baseline value is defined as the difference between the result collected/derived at a post-baseline visit/time point and the baseline value.

The change from baseline value at each post-baseline visit/time point will be calculated for all continuous parameters using the following formula:

$$\text{Change from Baseline Value} = \text{Result at Visit/Time Point} - \text{Baseline Value}$$

- The change of subcutaneous fat thickness and fat volume from baseline value at a post-baseline visit/time point will be calculated using the following formulas:

$$\text{Change of Subcutaneous Fat Thickness from Baseline Value} = \text{Subcutaneous fat thickness value at Visit/Time Point} - \text{Subcutaneous fat thickness value at Baseline}$$

$$\text{Change of Subcutaneous Fat Volume from Baseline Value} = \text{Subcutaneous Fat Volume value at Visit/Time Point} - \text{Subcutaneous fat volume value at Baseline}$$

The change from baseline value will only be calculated if the specific post-baseline visit/time point result and the baseline value for the parameter are both available and will be treated as missing otherwise.

- Percent Change from Baseline: The percent change from baseline value is defined as the difference between the result collected/derived at a post-baseline visit/time point and the baseline value and then divide by the baseline value which will be multiplied by 100 to display as a percentage.

The percent change from baseline value at each post-baseline visit/time point will be calculated for all continuous parameters using the following formula:

$$\text{Percent Change from Baseline Value} = \frac{\text{Result at Visit} - \text{Baseline Value}}{\text{Baseline Value}} \times 100$$

The percent change from baseline value will only be calculated if the specific post-baseline visit/time point result and the baseline value for the parameter are both available and will be treated as missing otherwise.

- **Study day:** The study day of an event is defined as the relative day of the event starting with the date of the first study drug administration (reference date) as Day 1 (there will be no Day 0).

The study day of events occurring before the first study drug administration will be calculated as:

$$\text{Study Day} = (\text{Date of Event} - \text{Date of First Study Drug Administration})$$

For events occurring on or after Day 1, study day will be calculated as:

$$\text{Study Day} = (\text{Date of Event} - \text{Date of First Study Drug Administration}) + 1$$

Study days will only be calculated for events with complete dates and will be undefined for events that are ‘Ongoing’ at the end of the study.

Relative days compared to an alternative reference point will be calculated similarly, but the alternative starting reference start date will be used instead of the date of the first study drug dosing.

- **Prior Medications:** Prior medications are defined as any medication where the use was stopped prior to the first administration of the study medication.
- **Concomitant Medications:** Concomitant medications are defined as any medication (other than the study drug) that was used at least once after the first administration of the study drug. Medications that were stopped on the same date as the first study drug administration will be defined as concomitant medications. If a clear determination cannot be made (partial medication end dates) the medication will be classified as concomitant
- **Treatment Emergent Adverse Events (TEAEs):** TEAEs are defined as adverse events that occurred following the first administration of study medication.
- **Treatment related TEAEs:** Treatment related TEAEs include the TEAEs which are deemed definitely, probably, or possibly related to study drug.
- **Conversion of categorical values:** In some instances, continuous variables are expressed as a range (i.e. < 10). In such cases, values may be converted to the range boundary (upper or lower limit as applicable). As an example, a value of <10 may be converted to 10. Such substitutions will be clearly documented in the footnotes of relevant outputs.

3.3 Multiple Comparisons and Multiplicity Adjustments.

All analyses will be performed without adjustment for multiple endpoints.

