14.2. Adverse and Serious Adverse Events

In this study, AEs will be reported for all subjects from the time of consent until the completion of the EOS/ET visit. SAEs will be reported for all subjects (enrolled and not enrolled) from the time of consent. Adverse events reported from the time of consent to pre-dose on Day 1 will be recorded as pre-treatment AEs. Treatment emergent- AEs will be evaluated from the first administration of IP until the EOS/ET visit. Adverse events that are deemed related to treatment and are ongoing 14 days post EOS/ET visit for non-serious AEs and 60 days post EOS/ET visit for serious AEs, the AE outcome will be recorded (e.g. Not Recovered or Recovering) depending on the status and entered on the AE eCRF page (see [Section 14.2.1.4](#)).

All spontaneously volunteered and enquired for, as well as observed AEs, will be recorded in the subject's medical records and the eCRF.

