14.2.4. Notification of a Serious Adverse Event

In order to meet the requirements for expedited reporting of SAEs meeting specific requirements to applicable regulatory authorities and institutional ethics committees, all SAEs, **must be reported to Sponsor or Sponsor’s representative within 24 hours** from the time the site investigational team first become aware of the event.

Initially reporting is achieved by completing an SAE report form and email to the Sponsor or their representative via the assigned project email address, which will be provided upon study setup.

If completion of an SAE form and emailing is not possible, reporting by telephone to Sponsor or their representative is required, and a completed SAE form must be emailed at the first opportunity.

Initial notification of an SAE by telephone to Sponsor must be confirmed in writing 24 hours from the time the site investigational team first becomes aware of the event using the SAE report form as described above.

As further information regarding the SAE becomes available, such follow-up information should be documented on a new SAE report form, marked as a follow-up report, scanned and emailed to the address at the bottom of the report form.

Withdrawal from the study in the event of an SAE and therapeutic measures taken shall be at the discretion of the Investigator. A full explanation for the discontinuation from the study should be made in the subject’s medical records and in the eCRF.

14.2.5. Clinical Laboratory Abnormalities and Other Abnormal Assessments as Adverse Events and Serious Adverse Events

Abnormal laboratory findings (e.g. biochemistry, hematology, and urinalysis) or other abnormal assessments (e.g. ECG and vital signs) per se are not reported as AEs. However, those abnormal findings that are deemed **clinically significant** by the Investigator and/or delegate or are associated with signs and/or symptoms must be recorded as AEs if they meet the definition of an AE (and recorded as an SAE if they meet the criteria of being serious) as previously described. Clinically significant abnormal laboratory or other abnormal findings that are detected after consent or that are present at Baseline and worsen after consent are included as AEs (and SAEs if serious).

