3.4 Handling of Missing Data

For the classification of Treatment emergent adverse event (TEAE) and Concomitant medication, the following will be applied in the following order:

- a. If all dates/times (start and stop) missing, the event/medication will automatically be classified as a TEAE/Concomitant medication.
- b. For AEs with a missing start date/time, if the event end date/time is prior to first study drug administration, the event will not be classified as a TEAE.

- c. If only the AE start year/ medication end year is present and is the same or is after the first study drug administration year unit, the event/medication will be classified as a TEAE/Concomitant medication.
- d. If the AE start month and year/medication end month and year are present and are the same or after the first study drug administration month and year units, the event/medication will be classified as a TEAE/Concomitant medication.

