11.1 Adverse Events

AEs and serious AEs (SAEs) are defined in the study protocol.

Treatment Emergent Adverse Events (TEAEs) are defined as adverse events that occurred following the first administration of study medication. If missing dates or time prevent a clear determination as to whether the AE is treatment emergent, the adverse event will be regarded TEAE.

All AE verbatim terms will be coded using the most recent version of MedDRA. All AE summaries will be restricted to include TEAEs only. AEs occurring prior to first dose of study medication will be listed but not included in any tabulations. Summary tables will include the number of participants (%) experiencing an event and the number of events. Participants will be counted only once for each SOC and PT level (categorical descriptive analysis).

The TEAE summaries will include:

- Overall summary of TEAEs.
- Summary of TEAEs by SOC, PT and Relationship.
- Summary of TEAEs by SOC, PT and Severity.
- Summary of Definitely Related TEAEs by SOC, PT and Severity
- Summary of Probably or Possibly Related TEAEs by SOC, PT and Severity
- Summary of TEAEs of Special Interest by SOC, PT and Severity
- Summary of serious TEAEs by SOC and PT.
- Summary of Treatment Related serious TEAEs by SOC and PT
- TEAE summary of events leading to the study drug withdrawal by SOC and PT.
- Treatment Related TEAE summary of events leading to the study drug withdrawal by SOC and PT

For the 'Overall Summary of TEAEs', the following items will be included:

1. Any TEAEs
2. Any serious TEAEs
3. Any TEAEs leading to study discontinuation
4. Any TEAEs of special interest
5. Any related TEAE
6. Any TEAEs leading to study discontinuation
7. Any TEAEs leading to death

All AEs will be listed and will include the start and stop date and time of AEs, AE number, verbatim term, Preferred Term, System Organ Class, SAE/TEAE flag, actions taken for AE, relationship to study treatment and outcome.

Separate by-participant data listings will be created for SAEs, AEs leading to study discontinuation, and AEs leading to death. These listings will be presented by participant ID and AE start date/time for the Safety Population.

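### The TEAE definition has no worsening clause, so an AE opened before first dose that later worsens or becomes serious can be missing from all 20 AE tables

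*SAP*

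**What the plan says.** **Definition.** SAP 3.2 states that "TEAEs are defined as adverse events that occurred following the first administration of study medication", and SAP 11.1 repeats it. Neither section mentions an AE that was already present and then increased in severity or became serious.

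**How status is decided.** SAP 3.4 works from the AE start date. One of its rules begins "If the AE start month and year/medication end month and year are present"; the end date settles an AE only when its start is missing. Where timing is unclear, SAP 11.1 has a default: "If missing dates or time prevent a clear determination as to whether the AE is treatment emergent, the adverse event will be regarded TEAE".

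**What is tabulated.** SAP 11.1 says "All AE summaries will be restricted to include TEAEs only" and also "AEs occurring prior to first dose of study medication will be listed but not included in any tabulations".

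**What the protocol adds.** Protocol 14.2 collects AEs from consent, and screening can last 28 days. It says: "Adverse events reported from the time of consent to pre-dose on Day 1 will be recorded as pre-treatment AEs". It gives no rule for relabelling such an AE if it later worsens. For the meaning of an AE the SAP defers to the protocol: "AEs and serious AEs (SAEs) are defined in the study protocol". Protocol 14.2.1 counts as an AE a rise in the frequency or intensity of a long-standing or recurring condition that the subject already had. Protocol 14.2.5 says that clinically significant abnormal findings "that are present at Baseline and worsen after consent are included as AEs (and SAEs if serious".

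**The concern.** A TEAE definition normally has two limbs: new events after first dose, and earlier events that get worse after first dose. The SAP has only the first. The AE tables are built entirely on TEAE status, so an event that fails the first limb has no other way into them.

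TEAEs are the first-named component of the Stage 1 primary endpoint and of the Stage 2 safety endpoint compared with placebo (Protocol 7.2). Stage 1 groups have 6 subjects each, so a single event is visible in a row. In the serious-TEAE tables, a single event may be the difference between an empty table and a non-empty one.

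**Working it through.** No sample size, power or alpha figure is involved, and the plan gives no figure to reproduce. The check follows one event through the rules, counts the tables affected, and sizes one event against the planned denominators.

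**1. Follow one event.** Take an acute clinical AE that starts during screening, is mild, is still open at the Day 1 dose, and becomes severe or serious two weeks later.

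- Protocol 14.2 labels it a pre-treatment AE.
- Protocol 14.2.6 asks for an onset, a resolution and an intensity for each AE. It does not say whether a change in grade or seriousness opens a new record or updates the existing one.
- *If a new record is opened* with a post-dose start date, SAP 3.2 and 3.4 make it a TEAE and it is tabulated.
- *If the original record is updated*, its start date is before first dose. It is not a TEAE, and SAP 11.1 keeps it out of every AE tabulation. The default for unclear timing does not rescue it, because no date is missing.

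Two sites in this multicenter study could therefore record the same event differently, and only one version would be counted.

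**2. Do the protocol's worsening provisions close the gap?**

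| Case | Covered? |
|---|---|
| Long-standing or recurring condition that increases in frequency or intensity | Yes, Protocol 14.2.1: the exacerbation is an AE |
| Significant abnormal laboratory or other finding present at Baseline that worsens | Yes, Protocol 14.2.5 |
| Acute clinical AE first reported in screening and open at Day 1 that rises in grade | Not clearly; the documents do not say whether it counts as a pre-existing condition |
| The same AE becoming serious without a change in frequency or intensity | Not covered by the exacerbation wording |

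Even in the first two rows, the event reaches a table only if the worsening carries its own post-dose start date.

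**3. Count the tables (SAP 17).**

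- Section 14.3.3: 10 AE displays × 2 stages = 20 tables, all restricted to TEAEs.
- Rest of section 14.3: 4 medication + 4 blood test + 2 urinalysis + 2 vital-sign + 4 ECG = 16 tables, none of which depends on TEAE status.
- Listings 16.2.7.1 (AEs) and 16.2.7.2 (SAEs) are titled without a TEAE restriction.

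**4. Size of one missed event.** Change in a row = 1 / planned group size:

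- Stage 1 dose group: 1/6 = 16.7 percentage points
- Stage 2 CBL-514: 1/50 = 2.0 points
- Stage 2 placebo: 1/25 = 4.0 points

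These are upper bounds for any one row. The row for any TEAE moves only if the subject has no other TEAE.

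**The case against.** The strongest reply is that the protocol already handles this. The SAP takes its AE definition from the protocol, and the protocol makes an exacerbation an AE in its own right. A post-dose exacerbation is then an AE that happened after first dose and meets the SAP definition as written. Protocol 14.2.1 also denies AE status only to fluctuations of existing conditions that do not worsen, which implies that worsening ones qualify. This stands for chronic or recurring conditions and for Baseline abnormalities, provided the worsening gets its own record. It does not settle the acute AE open from screening, or the AE that becomes serious.

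The second reply is that the affected group is small. The schedules in Protocol Tables 4 and 5 have no AE entry at Screening, and the screening and pre-dose procedure lists in Protocol 12 contain no AE review. This also stands, although Protocol 14.2 and 14.2.6 do call for collection from consent. Reactions to the injections themselves cannot start before dosing, so the main expected type of TEAE is untouched.

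A reader might draw four stronger inferences that the documents do not support:

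- *The event vanishes from every safety table.* Only the 20 AE tables are affected. The other 16 tables and the listings are not.
- *The loss is automatic.* It depends on a recording rule that neither document gives.
- *The rule favours CBL-514.* It can only lower the count within an arm, but it applies to both arms, so its effect on the Stage 2 difference has no fixed direction.
- *Safety oversight during the trial is weakened.* Under Protocol 8.3 the Safety Review Committee looks at all reported AEs, and under Protocol 14.2.4 every SAE goes to the sponsor within 24 hours. Neither depends on TEAE status.

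**Conclusion.** The point holds in a conditional form. The SAP classifies by start date, has no worsening limb, and bars pre-dose AEs from tabulation. A pre-treatment AE that stays on its original record and then rises in grade or becomes serious after dosing is therefore left out of all 20 AE tables, while remaining in the listings. The protocol shows that worsening is meant to count, and the SAP does not carry that intention through.

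The documents give no frequency for such events, and it is probably low. Per event, the effect on any one row is at most 16.7 points in a Stage 1 group, 2.0 points in the CBL-514 arm and 4.0 points in the placebo arm. These figures assume the planned group sizes of 6, 50 and 25, and that the subject is not already counted in that row. The conclusion also assumes that no eCRF completion guideline, which is not among the documents, already requires a new record when an AE worsens. The change is worth making because the rule as written can under-count post-dose harm and the repair is very cheap.

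**What to change.** 1. In SAP 3.2 and 11.1, define a TEAE as an AE with onset at or after the first study drug administration, or an AE with earlier onset that increases in severity or becomes serious after that administration.
2. State in SAP 11.1 that such an event is tabulated at its post-dose grade and seriousness, and limit the sentence barring pre-dose AEs from tabulation to AEs that do not meet the new second limb.
3. Instruct sites to enter a post-dose increase in grade, or a change to serious, of an AE already open as a new AE record with its own start date. This makes the second limb programmable, because a record holding one onset and one intensity cannot show when the change took place.

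The cost is one clause in two SAP sections and a short data-entry instruction, with no new assessments. The downside is slightly more data entry and possibly slightly higher TEAE counts.

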3.4 Handling of Missing Data

For the classification of Treatment emergent adverse event (TEAE) and Concomitant medication, the following will be applied in the following order:

- a. If all dates/times (start and stop) missing, the event/medication will automatically be classified as a TEAE/Concomitant medication.
- b. For AEs with a missing start date/time, if the event end date/time is prior to first study drug administration, the event will not be classified as a TEAE.

- c. If only the AE start year/ medication end year is present and is the same or is after the first study drug administration year unit, the event/medication will be classified as a TEAE/Concomitant medication.
- d. If the AE start month and year/medication end month and year are present and are the same or after the first study drug administration month and year units, the event/medication will be classified as a TEAE/Concomitant medication.

3.5 Coding of Events and Medications

Medical history and AE verbatim terms will be coded using the Medical Dictionary for Regulatory Activities (MedDRA) using the latest version available at the time of study commencement. Terms will be coded to the full MedDRA hierarchy, but the system organ class (SOC) and preferred terms (PT) will be of primary interest for the analysis.

Prior and concomitant medications will be coded using the World Health Organization Drug Dictionary using the latest version available at the time of study commencement. Medications will be mapped to the full WHO-DD Anatomical Therapeutic Chemical (ATC Level 4) class hierarchy, but PTs will be of primary interest in this analysis.

3.6 Treatment Groups

Descriptive analyses will display the following treatment groups:

Stage 1:

- CBL-514 320 mg
- CBL-514 480 mg
- CBL-514 640 mg
- CBL-514 800 mg
- Stage 1 Overall

Stage 2:

- CBL-514 600 mg
- Placebo
- Stage 2 Overall

Descriptive summary analysis of continuous and categorical variables will be conducted as described in section 3.1.

4. ANALYSIS POPULATIONS

In this study 3 analysis populations are defined: The Intent-to-Treat (ITT), Safety population and Per Protocol (PP).

Furthermore, any additional exploratory analysis not identified in the SAP will be identified in the final CSR as exploratory post hoc analyses, including analyses for additional study populations or subgroups of interest.

4.1 Population Descriptions

4.1.1 Intent-to-treat (ITT Population)

All assigned or randomized subjects, regardless of whether they receive treatment or not, will be included in the ITT population. Summaries, listings, and analyses by treatment group will be based on the subject's randomly assigned treatment, not what they actually received.

All demographic data analysis will be based on the ITT population. All listings will be presented by the ITT population.

4.1.2 Full Analysis Set Population (FAS Population)

The full analysis set (FAS) population will be defined as all randomized subjects who receive at least one course of IP and contribute qualified baseline and at least one post-dose efficacy assessment measured by ultrasound.

